1.1 Sickle Cell Disease

Sickle Cell Disease (SCD) comprises a group of red blood cell disorders and is the most common hereditary disease in the world, but rare in many developed countries. In the UK, SCD shows the greatest prevalence in people of African and Caribbean origin, and also affects people from Asian, Middle Eastern and Eastern Mediterranean descent.

[figure not shown]
SCD often leads to a chronic, life-long and debilitating illness in affected patients, characterised by morphological abnormalities in red blood cells (RBCs) and their distinctive 'sickle' shape. SCD results from inheritance of the sickle gene (for haemoglobin S) from both parents (haemoglobin SS), or a sickle gene from one parent and from the other parent, another abnormal haemoglobin gene such as, C or beta thalassaemia, that contributes to the clinical effect of the sickle gene.

Due to the role of haemoglobin in oxygen-binding within RBCs, mutations in the beta-globin subunits result in significant distortion and structural change to these cells in low oxygen conditions, which can in turn cause dangerous obstructions within blood vessels, reduced blood flow to vital organs, and a weakened immune system. The hallmark of SCD is severe pain experienced by patients, usually referred to as 'Vaso-Occlusive Crisis' (VOC), and other complications include severe anaemia, susceptibility to infections, splenic sequestration, acute chest syndrome, pulmonary hypertension, chronic organ damage, and stroke.

While it is possible for patients to be asymptomatic carriers of a single sickle cell gene, those who carry two genes can experience mild to more severe forms of the disease, in some cases resulting in a shortened life span and significantly impaired quality of life. With pain and symptoms often beginning during early childhood, SCD has significant impacts on both adult and paediatric patients, many children, particularly in developing countries, dying undiagnosed and untreated due to a lack of newborn screening programmes and inadequate access to healthcare.

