3.1 Primary Aim

The primary aim is to study the continuous pattern of vital parameters, collected over a long duration, within a sample cohort of consenting patients with SCD in order to determine how these relate to acute and chronic illnesses, as well as healthcare utilisation.

This will be through the creation of a unified data platform – comprising historical patient data, a full genetic background, and real-time patient data – through the incorporation of a wearable device into patient disease management.

Through this, the intended outcome will be improved quality and duration of life in patients.

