4.2 Data Sources, Access and Flow

From the starting point of sources including hospital Electronic Medical Records (EMRs), open data, and Hospital Episode Statistics (HES), the data platform will integrate written medical and primary care records from GPs, structured and unstructured EMIS/TPP records, as well as genetic information through external organisations such as 23andMe, following full patient consent. With additional wearables collected data (Section 4.3), these sources will be combined within a specialised SCD unified data platform to allow the application of a set of advanced algorithms, providing granular analysis of key patient metrics.

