7.2 Patient Withdrawal

Patients may voluntarily withdraw from the study at any time, as protected by GDPR, or be dropped from it at the discretion of the responsible clinician (investigator) at the NHS Trust. Patients may be withdrawn from the study if any of the following occur:

Patient or parent withdrew consent

Lost to follow-up

Death

Administrative problems

For patients who are lost to follow-up, the investigator will show 'due diligence' by documenting steps taken to contact the patient, such as dates of telephone calls, and mailings.

8. Statistical Analyses

An initial high-level investigation using descriptive analysis will be conducted across all variables in order to identify key trends and insights, from which further correlations and statistical significance will be tested. This will predominantly be performed using IBM SPSS Statistics 24 and Microsoft Excel, collected data analysed for outliers through Boxplot and Q-Q Plots, for normal distribution using Shapiro-Wilks testing, and for homogeneity of variance using Levene's testing. Due to the exploratory nature of the study, hierarchical stepwise regression of the outlined data points (Section 4.2 & 4.3) will be conducted, and any outliers detected through assumption testing will not be immediately excluded from analyses, instead further investigated to identify any clinically significant causes. For data that do not violate these assumptions, either independent t-tests (for experiments with two experimental groups) or one-way ANOVA (for experimental groups of 3 or more) will be performed, with Bonferroni post-hoc testing. Those that do violate these assumptions will undergo non-parametric Kruskal-Wallis testing. Each analysis will be based upon demographic variables, such as age and gender, correlated against genetic and clinical variables including hospital admissions, comorbidities, genotype, phenotype, and wearables collected data (Section 4.3). Those with p-values below 0.05 will be considered as statistically significant and undergo further study.

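### Section 8 tests genetic variables with methods that cannot adjust and names no ancestry variable, so a variant that only marks ancestry can be declared significant

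*Protocol*

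**What the plan says.** All references are to the protocol.

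- **Genetic data.** Section 3.1 builds the primary aim on a platform "comprising historical patient data, a full genetic background, and real-time patient data". Section 4.2 lists its sources, "as well as genetic information through external organisations such as 23andMe, following full patient consent".
- **Analysis.** Section 8 states that "hierarchical stepwise regression of the outlined data points (Section 4.2 & 4.3) will be conducted". Group comparisons use independent t-tests or one-way ANOVA, or Kruskal-Wallis where assumptions fail. Demographic variables are "correlated against genetic and clinical variables including hospital admissions, comorbidities, genotype, phenotype, and wearables collected data". Results with p below 0.05 count as significant and are taken further. Section 8 then says that the associations found will support the platform's predictive and treatment-pathway output.
- **Covariates.** The only demographic wording is: "Each analysis will be based upon demographic variables, such as age and gender". Ancestry, ethnic group and genetic principal components appear neither in Section 8 nor among the data points of Sections 4.2 and 4.3.
- **Population.** Section 1.1 says that SCD in the UK is most prevalent in "people of African and Caribbean origin, and also affects people from Asian, Middle Eastern and Eastern Mediterranean descent". Section 6 admits any patient with the diagnosis, within the age and consent criteria, and aims for a cohort that is as heterogeneous as possible.

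**The concern.** Variant frequencies can differ between ancestry groups. Outcomes such as admissions or wearable readings can also differ between the same groups for reasons unrelated to the variant. Where both hold, an unadjusted comparison of carriers with non-carriers partly compares ancestry groups. A variant with no effect then appears associated with the outcome.

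This is bias, not noise, so recruiting more patients makes such a false signal more likely to reach significance. The t-test, one-way ANOVA and Kruskal-Wallis named in Section 8 take no covariate. The stepwise regression could take one, but it draws on a list of data points that contains no ancestry item to select.

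What is at stake is false genetic leads passed to further study, and a predictive component that may carry over poorly from one ancestry group to another.

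**Working it through.** **The plan's own figure.** Section 4.1 sets 300 patients as 2% of the UK SCD population. 0.02 × 15,000 = 300 reproduces it; the lower end of the stated range gives 0.02 × 12,500 = 250. The figure is a recruitment target, not a power calculation. It is used here only as N.

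**Inputs.** From the protocol: N = 300 and the 0.05 threshold, taken as two-sided because the protocol does not say. Assumed, because the protocol gives none of them:
- two ancestry groups, with minority share m of 5% to 30%;
- allele frequency of 0.2 in both groups, 0.2 v 0.3, or 0.1 v 0.4;
- outcome shift d between groups of 0, 0.3 or 0.5 SD;
- no effect of the variant itself.

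**Formula.** With allele frequency p, the carrier proportion is 1 − (1 − p)². Let a₁ and a₀ be the minority share among carriers and non-carriers. The expected spurious difference is d × (a₁ − a₀). Dividing by its standard error gives k, and the false-positive rate is approximately P(Z > 1.96 − k) + P(Z < −1.96 − k).

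**Strongest setting (0.1 v 0.4, d = 0.5, m = 30%).**
- Carrier proportions: 1 − 0.9² = 0.19 and 1 − 0.6² = 0.64.
- All carriers: 0.7 × 0.19 + 0.3 × 0.64 = 0.325.
- a₁ = 0.192/0.325 = 0.591; a₀ = 0.108/0.675 = 0.160.
- Spurious difference: 0.5 × 0.431 = 0.215 SD.
- Variances, 1 + d²a(1 − a): 1.060 in carriers and 1.034 in non-carriers. Standard error: √(1.060/97.5 + 1.034/202.5) = 0.126.
- k = 1.70, so the false-positive rate is about 40%.

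**Weak setting (0.2 v 0.3, d = 0.5, m = 5%).**
- Carrier proportions 0.36 and 0.51; all carriers 0.3675.
- a₁ = 0.0255/0.3675 = 0.069; a₀ = 0.0245/0.6325 = 0.039.
- Spurious difference 0.015 SD, standard error 0.121, k = 0.13. The rate is about 5.2%.

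**Simulation (4,000 runs per setting, null variant, carriers v non-carriers).**

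| Allele frequency | Shift (SD) | Minority share | t-test | Kruskal-Wallis |
|---|---|---|---|---|
| 0.2 v 0.3 | 0.5 | 5% | 5.2% | 5.5% |
| 0.2 v 0.3 | 0.5 | 30% | 7.8% | 7.8% |
| 0.1 v 0.4 | 0.3 | 5% | 5.6% | 5.6% |
| 0.1 v 0.4 | 0.3 | 10% | 7.9% | 7.6% |
| 0.1 v 0.4 | 0.3 | 30% | 18.5% | 17.6% |
| 0.1 v 0.4 | 0.5 | 10% | 13.9% | 13.4% |
| 0.1 v 0.4 | 0.5 | 20% | 28.5% | 26.8% |
| 0.1 v 0.4 | 0.5 | 30% | 39.0% | 37.5% |

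With equal allele frequencies, or no outcome shift, the rate was about 5%. Linear regression with an ancestry term gave 4.1% to 5.4% across all settings, which is nominal within simulation error. The hand calculation agrees with the simulation at both ends.

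**The case against.** The strongest reply is that this is only an unwritten covariate. The demographic list in Section 8 is open, the regression is hierarchical and could carry a demographic block, and an analysis plan not seen here may name ethnic group. That stands for the regression: a reader might infer that the protocol rules ancestry out, and it does not. It does not answer the group tests, which the protocol fixes by name and which cannot adjust.

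A reader might also infer that the protocol calls the enrolled cohort multi-ancestry. Section 1.1 describes the UK patient population, and Section 6 asks for heterogeneity without mentioning ancestry. The cohort is drawn from that population, so a mixture is a fair expectation, but its proportions are unknown.

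Third, "genotype" in Section 8 may mean only haemoglobin genotype, which Section 1.1 uses to define the disease and which is not a null variant. The sentence can also be read as relating demographics to genetic data, not variants to illness. No variant list or genome scan is specified. This weakens the point without removing it, because Sections 3.1 and 4.2 bring in wider genetic data and Section 8 sends the Section 4.2 data into regression.

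Fourth, every magnitude is assumed, and the range includes no inflation. Nothing in the protocol shows that outcomes differ by ancestry among these patients. The simulation also used one variant and an exactly known ancestry indicator. It did not run stepwise selection, principal components or self-reported ethnic group, so it shows what adjustment can achieve, not what it would achieve here.

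Finally, the study calls itself exploratory and sends significant results to further study, which limits the harm.

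**Conclusion.** The point holds as a minor, conditional weakness. As written, Section 8 tests genetic variables with methods that cannot adjust, and with a regression whose listed inputs contain no ancestry item, in patients drawn from a population of several ancestries. False positives beyond the nominal rate arise only if variant frequency and outcome both differ by ancestry.

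Under the stated assumptions the rate per variant lies between about 5% (small minority share or similar frequencies) and about 39% (0.1 v 0.4, 0.5 SD shift, 30% minority share). More extreme allele frequencies would push it higher, but the protocol gives no ground for choosing them, or for preferring any value in the range. It would be wrong to conclude that the genetic findings will be false, or that the protocol forbids adjustment. What can be said is that the plan leaves a known source of bias unguarded when a standard safeguard is cheap.

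**What to change.** In Section 8:
- Test associations between genetic variables and outcomes only in regression models, or in analyses stratified by ancestry, and not by unadjusted t-test, ANOVA or Kruskal-Wallis.
- Force ancestry into each such model before any stepwise step. Use leading genetic principal components where the genetic file allows, and otherwise recorded ethnic group.
- Label any unadjusted genetic comparison as descriptive.

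In Section 4.2, add ethnic group as a data item, since it is not listed now and the format of the external genetic files is not stated.

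The cost is one data item, some wording and a few degrees of freedom; no extra patients are needed. Precision falls slightly for variants closely tied to ancestry, including haemoglobin genotype. Ethnic group is a coarser measure than principal components, so some confounding may remain where only it is available.

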4.1 Sample Size

There is an estimated 12,500-15,000 people living with SCD in the UK^{xvii}. Our patient sample size is based upon an estimated minimum proportion of the total population of patients with SCD we aim to enrol onto the digital platform and wearables pilot study, assuming not all patients will be reached by the initial programme launch through the Sickle Cell Society and partnering trusts, and that of those who are, not all will provide consent or be interested in participating. As such, our starting goal is to recruit 2% of the total UK SCD patient population, at 300 patients.

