An additional focus for the study regards data collected over extended periods of time and the progression of the disease state over this period, therefore requiring the inclusion of two independent variables. For such data, this will require Mauchly's test for sphericity in addition to Shapiro-Wilks testing for normal distribution. These data will then be tested for statistical significance using a two-way repeated measures ANOVA with a Bonferroni adjustment. Each step of the analytical output will be reported alongside changes in variance and F change, and collinearity of the independent variables will be investigated within the regression model.

This statistical analysis will in part feed into and be supported by the data platform's advanced AI and ML algorithms. However, the primary purpose of the AI technology will revolve around the predictive element of this study, highlighting potential outcomes and suggestions for optimal treatment pathways based upon the statistical analysis conducted, and key trends or associations identified.

9. Administrative Procedures

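### Section 8 asks about disease progression over time, but the repeated measures ANOVA it names ignores the order of the time points, so a significant result does not by itself show progression

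*Protocol*

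**What the plan says.** The second part of Section 8 (Statistical Analyses) sets out an additional focus on "data collected over extended periods of time and the progression of the disease state over this period". It holds that two explanatory factors are needed, and it prescribes checks of normality and, by Mauchly's test, of sphericity. The test itself is then fixed: "These data will then be tested for statistical significance using a two-way repeated measures ANOVA with a Bonferroni adjustment".

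Neither of the two factors is named. Time is the evident within-patient factor, and a sphericity test implies that it has at least three levels. The number of levels is not given. The section mentions no trend contrast, slope, continuous time term, direction or rate of change.

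Earlier in Section 8 the study is called exploratory: "Due to the exploratory nature of the study, hierarchical stepwise regression of the outlined data points" is planned, but it is not said to model change over time. The rule for results is "Those with p-values below 0.05 will be considered as statistically significant and undergo further study".

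**The concern.** Progression is an ordered change: later differs from earlier in a consistent direction. The time effect of a repeated measures ANOVA asks whether the time-point means differ in any way, and the group-by-time effect asks whether the group profiles differ in any way. Relabel the months in any order and both F values stay the same. This is so with complete data and sphericity met, so neither Mauchly's test nor better data capture addresses it.

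Two consequences follow. One atypical period can make the time effect significant with no progression at all. And because the test spreads its sensitivity over T-1 degrees of freedom, it is weaker than a 1-df trend test against small steady change, more so as the number of levels grows. Section 8 carries significant results into further study and lets the statistical analysis feed the platform's predictive algorithms, so a transient shift taken for progression could be passed on.

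**Working it through.** **Inputs from the protocol.** n = 300 (Section 4.1: "our starting goal is to recruit 2% of the total UK SCD patient population, at 300 patients"). This reproduces as 0.02 × 15,000 = 300, the upper end of the range in "There is an estimated 12,500-15,000 people living with SCD in the UK"; the lower end gives 0.02 × 12,500 = 250. Significance level 0.05 (Section 8). The protocol states no power, effect size or SD, so there is no power figure to reproduce.

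**Assumptions.** Complete data; within-patient SD 0.7 (variance 0.49), with between-patient SD also 0.7, so total SD is about 1; independent residuals; a slope common to all patients; T = 4, 12 or 52 time levels. Only the time effect is computed, because the second factor is not named.

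**Formulas.** The omnibus F has T-1 and (T-1)(n-1) degrees of freedom and noncentrality λ = n × Σ(μ_t − mean)² / 0.49. For a linear drift of total size D, Σ(μ_t − mean)² = D² × T(T+1) / [12(T−1)]. The 1-df linear contrast has the same λ for a linear drift, but all of it falls on one degree of freedom.

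**Steady drift.** D is chosen so that the linear contrast has about 80% power (λ about 7.8). At T = 12: 300 × 0.104² × 1.182 / 0.49 = 7.83.

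| T | D | Linear contrast | Omnibus F |
|---|---|---|---|
| 4 | 0.152 | about 80% | 64% |
| 12 | 0.104 | about 80% | 41% |
| 52 | 0.053 | about 80% | 19% |

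Larger drifts at T = 12:
- D = 0.15: λ = 16.3, omnibus power 78%
- D = 0.20: λ = 28.9, omnibus power 97.5%
- D = 0.30: λ = 65.1, omnibus power over 99.9%

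If the Bonferroni adjustment covers all T(T−1)/2 pairs (66 at T = 12), the first-versus-last comparison has noncentrality 0.104 / √(2 × 0.49/300) = 1.82 and about 6% power at the drift where the trend test has 80%. The protocol does not say that all pairs are compared.

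**One shifted month, no trend, T = 12.** For a shift d in one month common to all patients, Σ(μ_t − mean)² = d² × 11/12. If entry staggered over three months spreads the shift evenly over three study-month levels, it is 3(d/3)² − d²/12 = d²/4.

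| d | λ, one month | Omnibus rejects | λ, spread over three | Omnibus rejects |
|---|---|---|---|---|
| 0.10 | 5.6 | 29% | 1.5 | 10% |
| 0.15 | 12.6 | 65% | 3.4 | 18% |
| 0.20 | 22.4 | 92% | 6.1 | 31% |

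The linear contrast rejects about 5% of the time if the shifted month is in the middle. If it is the first or last month, λ = 300 × (5.5d)² / (143 × 0.49) = 1.3, 2.9 and 5.2, and the linear contrast rejects 21%, 40% and 62%.

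**Other correlation structures.** These are simulations at T = 12 with a Greenhouse-Geisser correction. With total SD 1, AR(1) correlation and a drift of 0.2, the omnibus test has 59% against 75% for the trend test (correlation 0.5) and 62% against 67% (correlation 0.8). With the drift re-sized so that the trend test has 80%, the omnibus test has:
- 59% with slope SD 0.5 and no serial correlation
- 67% with AR(1) 0.5 and a common slope
- 70% with AR(1) 0.5 and slope SD 0.3
- 78% with AR(1) 0.5 and slope SD 1.0

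**The case against.** The strongest case for the plan has four parts.

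- *The disease is episodic.* Section 3.1 asks about a continuous pattern of vital parameters and Section 4.5.2 about patterns and changes over time in general. The protocol nowhere defines progression as linear or monotone, so a test open to any pattern is defensible. This stands as a reason to keep the omnibus test, but not as a reason to let it answer the progression question alone.
- *The power loss depends on the assumptions.* It stands that serial correlation and varying slopes reduce the loss, in some settings to a few points, and that 52 levels is an extreme case the protocol does not state.
- *The shock has to hit the same study month for everyone.* The Section 5 timetable has a three-month column that appears to be enrolment, although its layout is broken in the text available. Staggered entry then dilutes a calendar shock, as the second half of the shift table shows.
- *A linear contrast is part of the same ANOVA and could be specified in a SAP.* Nothing in Section 8 forbids it. But the protocol pairs a named question with a named test, and that pairing does not match.

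A reader might infer that the plan would overlook steady progression. The figures do not support that: at 12 levels under the base assumptions, drifts of 0.20 or more are detected almost always. Nor does the protocol say that a significant time effect will be reported as progression; Section 8 calls the work exploratory and sends such results to further study.

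**Conclusion.** The mismatch holds in a limited form. An order-blind test is fixed for a question about ordered change, so significance alone does not show progression, direction or rate. For small steady change the power cost under the base assumptions is about 16, 39 and 61 percentage points at 4, 12 and 52 levels (80 minus 64, 41 and 19). It largely disappears for drifts of 0.20 or more at 12 levels, and it shrinks with serial correlation or varying slopes. The exposure to a one-off shift is real, but its size depends on whether the shift falls in the same study month for all patients.

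The number of levels, the SD, the correlation and the drift are all assumptions. A two-way design also tests the second factor and its interaction with time, and the Bonferroni adjustment acts on the follow-up comparisons without changing the omnibus null. As this is an exploratory, additional-focus analysis, the point is worth correcting but of modest severity.

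**What to change.** In Section 8, make the test of progression the linear time effect. This can be a pre-specified 1-df linear contrast within the planned ANOVA, or time as a continuous term in a mixed model with patient-specific intercept and slope. Name the second factor, and test group differences in progression by the group-by-linear-time term. Report the estimated rate with its direction. Keep the omnibus test for any pattern of change, and state that an omnibus effect alone is not reported as disease progression.

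The cost is wording only; no further data are needed. The downside is that a linear term is less sensitive to a non-monotone course and is itself affected by a shift in the first or last period, so the shape of the trajectory should also be examined, for example by plotting the means or adding a quadratic term.

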Ensuring that the quality of life, patient experience, and treatment options available to those living with SCD forms the focal point of this work. A critical part of this will revolve around the collation and real-time monitoring of data from multiple clinical sources, both from more traditional databases such as EMR, as well as expansion to include wearable data collection, ensuring patients and clinicians have access to this information in an easily visualisable way within a unified data platform. Through this, the aim of this research is to improve the collection, analysis and comprehension of SCD natural history and acute and chronic complications in terms of pain and symptoms, and to provide deeper understanding and management of the impacts and patient outcomes of the disease, outside of limited interactions with hospitals or clinics.

2.1 Data Limitations in Understanding Sickle Cell Disease's Natural History & Intervention Best Practice

There are significant challenges in fully understanding the natural history of SCD or the events surrounding a VOC, given the rare nature of the disorder and limited patient contacts within a healthcare setting. SCD is often considered an “invisible disease”, and patients are not always given the full understanding of their condition needed to effectively manage it in day-to-day life. Furthermore, much of the burden in monitoring symptoms and disease progression falls upon patients themselves, mood or pain diaries forming a substantial source of information for clinicians. Previous studies incorporating mobile health tools in supporting patients with SCD have highlighted the issue of adherence in self-monitoring and managing symptoms in such a way, reporting a mean compliance rate over the 28-day study period of 75.0%, peaking at 85.7% in week 1 and dropping to 57.9% in week 4^{vi}. These studies used mobile devices requiring the patient to log in and enter information every day over a short time period. The resulting information gathered therefore captures only short periods of time, with a low proportion of patient coverage, and emphasises the need for systems through which data can be collected from patients during their everyday life, in the long-term, and without pushing responsibility onto the shoulders of patients.

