4.5.2 Digital Data Platform and Wearables Pilot

Patients who enrol onto the pilot trial, either as a follow on from the patient focus groups or through recruitment via the Sickle Cell Society, London North West University Healthcare NHS Trust, or Barts Health NHS Trust, will be able to use either their own existing device or will be provided with a comparable market available smartwatch by the study. Data points, as summarised in Section 4.3, will be collected in an automated fashion on an ongoing basis, before transmission to a secure cloud database. This provides a novel approach to the monitoring of SCD that forgoes the need for patients to manually record information themselves and provides the potential for a larger patient cohort through remote monitoring, collecting a greater wealth of more in-depth, real-time and longitudinal data from patients during their daily lives. This supports a higher degree of compliance through decreased intrusion and an improved quality of data through improved objectivity and the elimination of retrospective recall. Furthermore, the utilisation of a wearable device provides the establishing of a baseline identified by 24/7 monitoring of data collection, providing a precise comparison for any patterns and changes over time to inform improved treatment pathways.

Patients will be set up with an electronic account and access to the digital platform through which their personal data can be accessed and visualised, and any additional metrics – such as body weight, dietary intake, emotional wellbeing, and additional medication consumption – can be manually input by the patient themselves as desired.

5. Project Plan

As part of the process of engaging patients prior to the full study and technology pilot trial, the project entails a series of initial pre-study patient focus groups over a 2-month period, in order to gather the relevant insights to ensure the study design, steps and outcomes are curated around a patient-centric outlook. Our intended timetable is as follows:

Project Stage	2 months	3 months	12 months				1 month
1 Pre-Study Focus Groups Engaging patients in study development prior to initiation of the full wearable pilot							
2 Pilot Study Enrolment Patients recruited to participate in the pilot through pre-study focus groups, the Sickle Cell Society & participating trusts							
3 Wearables Pilot Study Trialling of the live wearable and digital platform with patients, data collection, and analysis							

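### Section 8 fixes a two-way repeated-measures ANOVA for the longitudinal data, a method that discards every patient with a gap in the series; a mixed model on all available data would fit better

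*Protocol*

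**What the plan says.** Section 8 of the protocol sets apart "data collected over extended periods of time and the progression of the disease state over this period" and prescribes a fixed chain of tests for it. First: "For such data, this will require Mauchly's test for sphericity in addition to Shapiro-Wilks testing for normal distribution". Then: "These data will then be tested for statistical significance using a two-way repeated measures ANOVA with a Bonferroni adjustment". No other method for repeated measurements is named. The paragraph speaks of two independent variables without saying which they are, and it gives no unit for the time factor.

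This matters for the main question, because the primary aim (Section 3.1) concerns long-run patterns of vital signs and how they relate to illness and use of health care.

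The data are described elsewhere. In Section 4.5.2, wearable data points "will be collected in an automated fashion on an ongoing basis", further items are entered by patients when they wish, and participants "will be able to use either their own existing device or will be provided with a comparable market available smartwatch by the study". Section 7.2 allows withdrawal at any time and lists loss to follow-up and death as reasons for leaving. On numbers, Section 4.1 says that "our starting goal is to recruit 2% of the total UK SCD patient population, at 300 patients".

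**The concern.** Classical repeated-measures ANOVA is built for balanced experiments. Every patient must be measured at the same set of occasions, and a patient with one empty cell is removed entirely. A patient who withdraws late in the pilot would contribute nothing, despite months of usable data.

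Ongoing ambulatory data from up to 300 people will not form a complete rectangle unless they are first reduced to coarse summaries. Even then, withdrawal leaves empty cells. Two things are at stake. One is precision, because usable data are thrown away. The other is selection: if non-wear or withdrawal is related to illness, patients with complete series differ from the cohort in the very respect under study.

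There is a second, narrower problem. The chain requires Mauchly's test, which exists only when there are enough complete patients for the number of time levels.

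**Working it through.** **Inputs from the protocol.** Recruitment goal 300 (Section 4.1). Section 4.1 gives its basis: "There is an estimated 12,500-15,000 people living with SCD in the UK". The pilot lasts about 12 months (Section 5; the timetable is broken in the text at hand, so matching the 12-month column to the wearables stage is an assumption). This gives 365 daily, 52 weekly or 12 monthly levels.

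**The plan's own figure.** 0.02 × 15,000 = 300, so the goal is reproduced at the upper end of the range; the lower end gives 0.02 × 12,500 = 250. It is a recruitment target, not a power calculation.

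**Inputs that are assumptions.** The protocol gives no completeness figure for this study. Two illustrative values of completeness per occasion, q, are used: 96%, the adherence quoted in Section 2.4 from an activity-tracker study in breast cancer, and 75%, the mean compliance quoted in Section 2.1 from a manual diary in sickle cell disease. Neither measures completeness per occasion on this study's devices.

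**Patients with a complete series of k occasions.**
- Independent gaps: 300 × q^k. For example, 300 × 0.96^12 = 183.8, 300 × 0.96^52 = 35.9 and 300 × 0.75^12 = 9.5.
- Gaps clustered within patients (beta-binomial, within-patient correlation r): 300 × B(a + k, b) / B(a, b), where B is the beta function, a = q(1/r − 1) and b = (1 − q)(1/r − 1), with r = 0.3 and 0.6.
- Upper bound, if all gaps fall in the same patients: 300 × q.

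| q | Levels | Independent | Clustered, r = 0.3 to 0.6 | Upper bound |
|---|---|---|---|---|
| 96% | 365 daily | 0 | 183 to 247 | 288 |
| 96% | 52 weekly | 36 | 219 to 260 | 288 |
| 96% | 12 monthly | 184 | 248 to 271 | 288 |
| 75% | 365 daily | 0 | 12 to 86 | 225 |
| 75% | 52 weekly | 0 | 38 to 119 | 225 |
| 75% | 12 monthly | 10 | 85 to 151 | 225 |

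To keep half the patients under independent gaps, q must be at least 0.5^(1/k): 99.8% daily, 98.7% weekly, 94.4% monthly.

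**Mauchly's test.** The covariance matrix of the k − 1 time contrasts must be non-singular, so n − g ≥ k − 1, where n is the number of complete patients and g the number of between-patient groups.
- Daily: 364 contrasts against at most 300 − 1 = 299 error degrees of freedom (298 with two groups). The test cannot be computed even with no missing data. With two groups it needs 366 complete patients.
- Weekly: 51 contrasts, so 53 complete patients are needed with two groups. It is computable at n = 300, where the simulated type I error at the 5% level was about 4% (400 runs). The approximation deteriorates as complete cases fall: about 19% at 100 and 94% at 60. The 36 complete patients in the table's independent-gap case would be too few (36 − 2 = 34, below 51).
- Monthly: 11 contrasts, 13 complete patients needed. It is computable at n = 300.

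**The case against.** The strongest defence is that Section 8 names no time unit, and the detail may sit in a statistical analysis plan that is not at hand. Weekly or monthly summaries of a continuous stream would absorb charging breaks and short non-wear, and Mauchly's test would then be computable at n = 300. Even where it is not, a univariate F test with an epsilon correction remains possible. The study also calls itself exploratory, and significant results only lead to further study. All of this stands, and it limits the size of the point. It does not rescue the method: deletion of incomplete patients persists under any time unit, and Section 8 prescribes the sphericity test without stating a correction.

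Several stronger readings are tempting, but the protocol does not support them.

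- *Most patients would be lost.* A reader might infer this from Section 2.1, which cites compliance "peaking at 85.7% in week 1 and dropping to 57.9% in week 4". Those figures come from a diary needing daily log-in, the burden that automated collection is meant to remove, and low diary compliance is not dropout. The table shows that most patients can be kept, for instance with monthly levels at 96%.
- *The sphericity test is impossible.* That holds only on a daily grid, which Section 8 does not specify.
- *Standard errors are far too small because daily rows are pooled in the t-tests, ANOVA or regression.* Section 8 does not say that rows are pooled. It sends long-term data to the repeated-measures method, so the other tests can be read as one value per patient.
- *Device type cannot be adjusted for.* Section 8 includes regression, where device could be a predictor.
- *Both ANOVA factors must be within-patient.* The two factors are not named, and the term is often used for one repeated factor and one group factor.
- *A definite size of bias among completers.* Any such figure would need crisis rates and missingness odds that the protocol does not give.

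**Conclusion.** The point holds in limited form. The protocol commits its only longitudinal analysis, and with it the primary aim, to a method that needs complete, balanced series, while describing data that will have gaps and withdrawals. The loss ranges from small to nearly total: at 96% completeness, from 29 of 300 patients (monthly, strongly clustered gaps, 271 kept) to all of them (daily, independent gaps). At 75% with monthly levels, 149 to 290 would be lost. These ranges rest on assumed completeness and assumed gap patterns.

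Selection bias follows only if gaps are related to illness, which is plausible here but not quantified. The failure of Mauchly's test is certain for a 12-month daily grid at 300 patients and does not arise at n = 300 with weekly or monthly levels. Because the study is exploratory and no confirmatory test depends on this step, the change is worth making before analysis, but the severity is moderate.

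**What to change.** In Section 8, state the time unit for the longitudinal analysis. Replace the Mauchly and repeated-measures ANOVA step with a linear mixed-effects model, or a generalised one for counts and binary outcomes, fitted to all available observations. It should have patient random effects, a suitable within-patient correlation structure, and age, sex, genotype and device type as fixed effects. Wherever any other analysis uses more than one row per patient, either account for clustering by patient or reduce the data to one summary per patient first.

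The cost is a change of wording and slightly more modelling work; mixed models are available in the statistics package that Section 8 names. The trade-off is reliance on a missing-at-random assumption, which should be stated. If non-wear depends on unrecorded illness at the time, the mixed model will not remove all of the bias. It does still use every patient with at least one measurement and needs no sphericity test.
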